For HIC Use Only**Date Approved****Human Investigation Committee Signature****This protocol is valid through** _____**SECTION V: RESEARCH PLAN**

1. **Statement of Purpose:** State the scientific aim(s) of the study, or the hypotheses to be tested. Well-controlled randomized clinical trials of computer-assisted therapies are very rare, and there are few that would meet current methodological standards established for traditional evidence-based treatments. We propose to conduct a randomized clinical trial of our web-based version of Computer Based Training in Cognitive Behavioral Therapy (CBT4CBT) to evaluate its effectiveness relative to therapist-delivered cognitive behavioral therapy or standard outpatient counseling with participants with alcohol use disorder. Specific aims are as follows:

Aim 1 – Evaluate the efficacy of CBT4CBT and clinician-delivered CBT relative to standard treatment for reducing alcohol use through an 8-week randomized trial with 6-month follow-up. Our primary hypothesis is that either form of CBT will be more effective than standard treatment at increasing the percentage of days abstinent (PDA)^{2, 3} during treatment (8 weeks) and through the follow-up (6 months), assessed via Timeline FollowBack interviews^{4, 5}. Secondary outcomes will include percentage of heavy drinking days (PHDD)^{6, 7}, urine ethyl glucoronide analysis (EtG)⁸⁻¹⁰, drinking-related consequences^{11, 12}, quality of life¹³, and cost effectiveness¹⁴.

Aim 2 – Evaluate the extent to which CBT's putative mechanisms act as mediator of treatment effect on reducing alcohol use in both forms of CBT relative to standard treatment.

Hypothesized mechanisms include enhanced behavioral, cognitive, and affective control, measured within treatment by indices reflecting acquisition and implementation of targeted skills (behavioral role-play assessment¹⁵, coping strategies inventory^{16, 17}, and measures of homework completion and knowledge of CBT). Latent growth curve modeling will test for mediation using the product of coefficients method^{18, 19}. We hypothesize:

- (a) greater increases in skills acquisition for those assigned to either form of CBT compared to TAU;
- (b) increased acquisition of skills during treatment will be associated with greater PDA during follow-up;
- (c) CBT's effect (in either delivery format) on PDA will be mediated by skills acquisition.

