[name] led the team that developed the adaptation of CBT4CBT specifically targeting alcohol use, which was completed in 2011. The program follows the format used in the original drug-based version, with content, situations, and videos adapted for individuals with alcohol use disorders and based closely on the NIAAA CBT manual¹²⁵. *We have completed an R21 trial establishing its feasibility, safety, and preliminary efficacy at reducing alcohol use within a sample of outpatient treatment seekers (PRELIMINARY DATA – C.1.e.). The next logical step in this program of research is a larger randomized controlled trial, which would include traditional clinician-delivered CBT and treatment as usual (TAU) in order to evaluate whether the computerized version retains key characteristics of clinician-delivered CBT.* Although a direct comparison of CBT4CBT to clinician-delivered CBT (e.g., a non-inferiority study)¹²⁶⁻¹²⁸ would be premature at this stage (and not sufficiently powered in the proposed project), such a design could compare the cost-effectiveness of the two formats, as well as generate effect size and power estimates for a future non-inferiority trial. *Additionally, this*

design is an ideal platform to evaluate mechanisms of CBT, for several reasons^{65, 129}. First, inclusion of a treatment condition consisting of CBT4CBT delivered with minimal clinical contact (*focused on monitoring clients' safety and assessing signs/symptoms of clinical deterioration*) would offer the evaluation of an isolated form of CBT's main active ingredient - coping skills training, without the presence of therapist factors and common factors associated with clinician-delivered CBT. Second, although both delivery formats of CBT may facilitate change through similar mechanisms (e.g., enhanced affective, behavioral, and cognitive control), the processes by which they affect these mechanisms may differ in several ways. For instance, there is likely to be a larger 'dose' of CBT skills training in the computer-delivered version. It is also possible that the interpersonal and tailored discussion of completed homework activities may facilitate out-of-session practice in clinician-delivered CBT, whereas viewing the video-based modeling of skills implementation may be most salient in CBT4CBT. Third, retaining a TAU condition is essential for both evaluating the efficacy of CBT4CBT for alcohol use disorders, as well as permitting evaluation of the specificity of CBT's mechanisms.

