Latent growth curve modeling will be the principal strategy for evaluating mediation using Mplus version 7²⁵¹. The product of coefficients method^{18, 19} will be

used to determine the mediating effects of skills acquisition during the treatment period *on PDA* during follow-up. In this model (Figure 4), M_1 through M_3 are repeated measures (weeks 0, 4, 8) of the mediator ‘acquisition of skills’ (as measured by ARRT¹⁵, CSI¹⁶, homework completion and quality, and knowledge assessment⁵⁰). Both the intercept (I_M) and slope (S_M) act as joint mediators of the effect of X (treatment condition) on Y (PDA during 6 month follow-up), allowing the examination of the average level (i.e., intercept) and average change over time (i.e., slope) of the mediator. We will be using the 6-month period following treatment as our alcohol use outcome in this model to support the temporal relation criterion⁶⁴, as well as to evaluate the delayed emergence of CBT’s effect on alcohol use¹³⁹. This model will test:

- **H2a:** Effect of CBT on acquisition of skills (a_2 path: $X \rightarrow M$): Clinician-CBT>TAU; CBT4CBT>TAU
- **H2b:** Effect of change in acquisition of skills on PDA by month during follow-up (b_2 path: $M \rightarrow Y$)
- **H2c:** Indirect effect of CBT on PDA via change in acquisition of skills ($a_2 * b_2 / se_{a2} * se_{b2}$)

Adequacy of sample size: Parameter estimates from our initial trial of CBT4CBT that supported coping skills acquisition as a mediator of treatment effects on substance use⁹⁶ were used to estimate effect sizes of treatment condition on PDA via skills acquisition ($a=.26$; $b=.59$). Based on these effect sizes and power estimates for testing mediation derived from a simulation study⁹⁴, we will have adequate power (.80) to detect significant mediating effects with the proposed sample size of 60 per condition.

Exploratory Aims:

[figure not shown]

(a) Pre-treatment cognitive function as indicated by measures from CANTAB tasks (sustained attention,

working memory, response inhibition, cognitive flexibility, planning, decision-making) will be evaluated as moderators of CBT's effect on PDA (clinician-delivered CBT and CBT4CBT vs. TAU), using linear moderation regression models, such that a significant interaction between pre-treatment cognitive function measures and treatment condition would indicate a moderated effect (i.e., the effect of CBT on PDA is dependent on levels of pre-treatment cognitive function);

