(b) Using a conditional process analysis²⁵², CANTAB measures at pre-treatment will be explored as a moderator of the effect of CBT on the acquisition of skills (i.e., moderated-mediation; Figure 5). In this model, baseline measures of cognitive function (W) moderate both the direct (c'_3) and indirect effects ($a_3 * b_1$) of CBT (X) on PDA (Y);

(c) (i) Using latent growth curve modeling outlined in Aim 2 we will explore differences in mediation across the two forms of CBT (clinician-delivered CBT vs. CBT4CBT) to evaluate the role of skills acquisition across formats; (ii) Additional potential mediators such as therapeutic alliance and self-efficacy²⁵³ will be explored across CBT delivery formats using serial multiple mediation models²⁵⁴; (iii) Pre-treatment cognitive function (CANTAB) will be evaluated as a moderator of the treatment effect on alcohol use outcomes across CBT delivery formats, as well as on the mediated effect of skills acquisition (moderated-mediation across CBT formats). Additional potential moderator variables will be explored across CBT formats, such as client motivation (Stages of Change Questionnaire), alcohol use severity (AUDIT) and general intelligence (Shipley) using linear moderation regression models.

3. Genetic Testing N/A

A. Describe

- the types of future research to be conducted using the materials, specifying if immortalization of cell lines, whole exome or genome sequencing, genome wide association studies, or animal studies are planned

No immortalized cells will be utilized or established. Genomewide association studies will be conducted.

- the plan for the collection of material or the conditions under which material will be received

Saliva samples will be collected from study participants by study staff.

- the types of information about the donor/individual contributors that will be entered into a database

Demographic information, diagnostic information and assessment and outcome responses will be entered into a database.

- the methods to uphold confidentiality

There will be no personal identifiable information associated with the biological materials (saliva sample and DNA). The biological material from subjects will be identified by code rather than by personal identifiable information

B. What are the conditions or procedures for sharing of materials and/or distributing for future research projects?

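### Aim 2 uses one skill-to-drinking path (b2) for all arms, so it cannot show whether that path holds in CBT as well as TAU, and the indirect effect is misstated for CBT if the paths differ

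*Combined protocol and SAP*

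**What the plan says.** Section V, Background A4 gives two reasons for the TAU arm: "retaining a TAU condition is essential for both evaluating the efficacy of CBT4CBT for alcohol use disorders, as well as permitting evaluation of the specificity". The specificity in question is that of the mechanisms by which CBT acts. In the Statement of Purpose, Aim 2 asks whether the putative mechanisms "act as mediator of treatment effect on reducing alcohol use in both forms of CBT relative to standard treatment", and hypothesis (c) is that CBT's "effect (in either delivery format) on PDA will be mediated by skills acquisition".

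Section C.2.f describes the Aim 2 model, and Section V item 11 repeats its hypotheses. It is a latent growth model in which the intercept and slope of skills "act as joint mediators of the effect of X (treatment condition) on Y (PDA during 6 month follow-up"). The three hypotheses treat the arms differently:

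- H2a (a2 path) names them: "Clinician-CBT>TAU; CBT4CBT>TAU".
- H2b (b2 path) names none: "Effect of change in acquisition of skills on PDA by month during follow-up".
- H2c is a single product of a2 and b2.

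The power statement likewise uses one b (a=.26, b=.59, power .80, 60 per condition).

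Two exploratory analyses come near the question. Exploratory (b) makes cognitive function the moderator and writes the indirect effect as a3*b1, so the b path is not moderated. Exploratory (c)(i) will "explore differences in mediation across the two forms of CBT (clinician-delivered CBT vs. CBT4CBT"), which leaves TAU out.

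**The concern.** A claim that CBT works through skills has two links: CBT raises skills more than TAU does, and skill change goes with less drinking among people given CBT. H2a tests the first against TAU. The second rests on a b2 estimated across all arms, which assumes no treatment-by-mediator interaction. Nothing described in the plan checks that assumption.

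Two errors are possible. If skill change matters mainly in CBT, the TAU participants dilute b2 and the mediated effect is understated. If skill change tracks drinking mainly in TAU, H2b and H2c can be significant and be read as CBT working through skills although the path is absent in the CBT arms. In both cases the TAU arm has not been used to examine specificity on the path that carries the mediation claim.

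**Working it through.** **Inputs from the documents.** a=.26, b=.59, 60 per condition and power .80 (C.2.f and item 11, Aim 2). Alpha .05 is stated for H1a and H1b only, and is assumed two-sided here.

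**Assumptions.** M = aX + e1 and Y = b(arm)·M + e2, with unit residual SDs, an observed mediator, no direct effect and no loss. Mediation is declared when both paths are significant (joint-significance test). The documents give no b by arm, so the arm-specific values are assumed.

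**Step 1: the plan's own figure.** With X standardised (equivalently coded -1/+1 at equal arms), 60 v 60 and one common b, simulated power is .814 (joint significance) or .786 (Sobel). This reproduces .80. Coding X as 0/1 with a=.26 gives only .30, so the stated power appears to rest on the first scaling. The CBT-TAU difference in M is then 2 × .26 = .52.

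**Step 2: what the common b2 estimates.** With equal mediator variance in the arms,

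b2(common) = w·b(TAU) + (1-w)·b(CBT), where w = n(TAU)/N.

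w is 1/2 at 60 v 60 (one CBT arm) and 1/3 at 120 v 60 (CBT arms pooled). The indirect effect is .52 × b2.

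| b in CBT / TAU | At CBT value | Common b2, 60 v 60 | Common b2, 120 v 60 |
|---|---|---|---|
| .59 / .59 | .52 × .59 = .307 | .307 | .307 |
| .59 / 0 | .307 | .52 × .295 = .153 | .52 × .393 = .205 |
| .59 / .295 | .307 | .52 × .4425 = .230 | .52 × .492 = .256 |
| 0 / .59 | 0 | .52 × .295 = .153 | .52 × .197 = .102 |

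Simulation agrees: .153 to .154 and .205 to .207 in the second row, .231 and .256 in the third. The understatement is 50% or 33% in the second row. In the third it is (.307-.231)/.307 = 25% or (.307-.256)/.307 = 17%.

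**Step 3: how often mediation is declared.**

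- b=0 in CBT and .59 in TAU: the common-b2 test is positive in about 68% of trials at 60 v 60 and 63% at 120 v 60. With the CBT-specific b2 it is positive in about 4%.
- b=.59 in CBT and 0 in TAU: power is .68 (common) against .80 (CBT-specific) at 60 v 60, but .905 against .907 at 120 v 60.
- b=.59 in CBT and .295 in TAU: power is essentially unchanged (.807 v .802 at 60 v 60; .906 v .906 at 120 v 60).

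**Step 4: price of freeing b2 when the paths are equal.** At 60 v 60 with an error-free mediator, power goes from .805 to .798, and the SD of the indirect effect from .118 to .128 (about 8%). With assumed mediator reliability .7, power goes from .659 to .618 (4 points); with .5, from .524 to .433 (9 points).

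**Step 5: power for the difference b2(CBT) - b2(TAU).** SE = sqrt(1/(n(TAU)-2) + 1/(n(CBT)-2)).

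- 60 v 60: sqrt(1/58 + 1/58) = .186. Difference detectable at 80% power: 2.80 × .186 = .52. Power for a difference of .295: about .36.
- 120 v 60: sqrt(1/58 + 1/118) = .160. Detectable difference: .45. Power for .295: about .45.
- For a difference of .59, simulated power is .88 (60 v 60) or .95 (120 v 60).

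**The case against.** The best defence is that a common b2 fits the plan's stated theory. The Background presents coping skills as generalizable, and hypothesis (b) links skill gain to abstinence without naming an arm. Where the Assessments section speaks of treatment-specific effects, it means the acquisition of skills. On that reading CBT is specific because it produces more skill, which H2a tests against TAU. The earlier-trial analysis in C.1.b also used one b adjusted for treatment. This defence stands in part: a reader might infer that the plan does not evaluate specificity at all, and H2a shows otherwise. It does not close the gap, because the mediation claim for CBT also needs the second link, and that link is assumed equal across arms without a check.

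A reader might also take the alliance results in C.1.d as evidence that b2 differs by arm. They are not. They concern alliance rather than skills, use different scales for a counselor and a program, and relate to cocaine outcomes. The documents give no estimate of b2 by arm.

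The scenarios with b=0 in one arm are extremes chosen to show direction and bound the size. With an interaction there are two indirect effects, at the TAU and CBT values of b, and the common product lies between them. The 63 to 68% is therefore a false-claim rate only for a statement about the CBT arms.

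Two further cautions stand. Exploratory (c)(i) could yield b paths within the CBT arms, although it is exploratory and omits TAU. The path diagram (Figure 4 of C.2.f) is not shown, so an interaction drawn only there cannot be excluded; the text and hypotheses name none.

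**Conclusion.** The point holds for Aim 2 as described in the text, and is confined to the b path and the product. H2a covers specificity of skill gain; nothing covers whether the skill-to-PDA path differs between CBT and TAU. The common-b2 product is unbiased if the paths are equal. Otherwise it misstates the indirect effect at the CBT value: by about 17 to 25% when b in TAU is half that in CBT, and by 33 to 50% when it is zero. In the reverse extreme, mediation would be declared in about 63 to 68% of trials with no skill-to-drinking path in CBT. These sizes rest on assumed arm-specific b values, equal mediator variances, and a scaling of a=.26 that reproduces the plan's .80.

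A reader might infer that the common-b2 model is wrong and should be replaced by a CBT-specific product. The documents do not support that: they give no evidence of unequal paths, and replacing the planned test would give up precision. The case is for an added, pre-specified analysis. The primary hypothesis (Aim 1) is unaffected.

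**What to change.** In C.2.f and Section V item 11, under Aim 2:

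1. Keep the common-b2 model as the planned test of H2b and H2c, on the stated power basis.
2. Pre-specify beside it a treatment-by-skill-slope term, or a multiple-group growth model with b2 free between TAU and CBT.
3. Report b2 and the indirect effect at the CBT and TAU values, and b2(CBT) - b2(TAU) with a 95% interval.
4. State that a claim that CBT works through skills will be made only if the CBT-specific b2 supports it.
5. Leave homework out of the cross-arm comparison if it is not collected in TAU. The treatment descriptions (C.2.d) mention it only for the two CBT arms.

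No new data or participants are needed. The cost is wording plus at least one extra parameter, and more if the two CBT arms are kept separate or the intercept path is also freed. The plan should state two downsides. The CBT-specific estimate is less precise: at 60 v 60 the power loss is under 1 point with an error-free mediator, but about 4 to 9 points at assumed reliability .7 to .5. The difference test has only about 35 to 45% power for a b difference of .295, so a null result is not evidence that the paths are equal.

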- Data from our recently completed R21 evaluating the alcohol version of CBT4CBT (including CBT4CBT delivered with brief clinical monitoring) indicates that this approach is feasible, safe and well-accepted by individuals with alcohol use disorders. *Preliminary data further indicate CBT4CBT is effective at increasing the percentage of days abstinent and the percentage of subjects with no heavy drinking days compared to standard treatment only.*
- Our published and preliminary data highlight the relevant experience and developing expertise of New Investigator [name] (PI), with respect to evaluation of mechanisms of behavior change in computerized CBT^{96, 122, 131, 153, 159, 163}.

C.2. RESEARCH PLAN

C.2.a. Overview

One hundred eighty individuals seeking treatment for alcohol use at the MCCA program in Bridgeport or New Haven, CT or SATU in New Haven will be randomized to (1) standard treatment as usual (TAU) at MCCA or SATU, (2) clinician-delivered CBT, or (3) CBT4CBT for alcohol use disorders (with brief clinical monitoring). Treatments will be delivered over an 8-week period with a six-month follow-up after termination of the study treatments, consistent with prior trials of CBT4CBT^{119, 122}. The primary outcome measure will be the percentage of days abstinent from alcohol (measured via Timeline FollowBack⁴), with secondary measures to include percentage of heavy drinking days, percentage of positive urine ethyl glucuronide (EtG), drinking-related consequences, quality of life, and cost effectiveness.

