- *Are physically dependent on alcohol, opioids or benzodiazepines such that immediate medical detoxification is necessary for safety purposes* (individuals demonstrating significant withdrawal symptoms would be eligible for re-screening following brief medical detoxification, which is arranged by MCCA or SATU staff at triage).

2. Rationale for sample choice. We are proposing relatively few exclusions that parallel our

completed trials of CBT4CBT^{119, 123} in recruiting a broad range of individuals whose primary substance use problem is alcohol (those with low levels of drug use will be eligible providing they do not meet current disorder criteria). *The inclusion criterion regarding level of drinking is consistent with NIAAA definitions of risky/heavy drinking^{167, 168} and comparable to prior randomized trials for establishing efficacy of cognitive behavioral treatments^{3, 28, 169}. We will exclude those initiating an alcohol pharmacotherapy to limit potential confounds, as well as exclude individuals experiencing significant alcohol withdrawal symptoms in need of medical detoxification for safety reasons.*

C.2.c. Procedures

1. Initial screening by Research Coordinator: All new MCCA or SATU patients will be invited to participate in the protocol at the time of their initial clinic appointment. See below for detailed description.

2. Urn randomization: To increase the likelihood that treatment groups are balanced with respect to demographic variables (gender, race, education) as well as likely prognostic variables (severity of alcohol dependence, level of familiarity with and access to computers) participants will be assigned to treatment conditions through urn randomization^{173, 174}, using a Microsoft Access program we have implemented successfully in multiple trials^{138, 142, 171, 175, 176}.

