1. Standard treatment as usual (TAU): Participants randomized to this condition will receive treatment-as-usual at MCCA or SATU. This typically consists of *group counseling delivered by masters-level and certified counselors trained and employed by MCCA or SATU and supervised by MCCA Clinic Director*, [name], or the SATU Clinical Director, [name]. Patients in this and all conditions are offered standard ancillary services, delivery of which is monitored closely throughout the trial (see Assessments).

2. Individual clinician-delivered CBT: Participants assigned to this condition will receive 8 weekly individual sessions of manual guided CBT^{120, 125}, which provides detailed instructions to clinicians regarding the same topic areas covered in CBT4CBT. Clinicians will be trained and supervised using procedures we have developed in multiple previous CBT trials⁵⁰,

^{136, 138} to protect internal validity and treatment integrity. Extensive procedures for clinician selection, training, and supervision should minimize variability in outcome due to ‘therapist effects’¹⁸³, however as noted earlier, some level of clinician variability is expected. The CBT clinicians will be at least masters-level clinicians drawn from MCCA or SATU staff and selected on the basis of audio-taped samples of their work. Following an initial 2-day didactic training, they will each complete at least 3 closely supervised training cases on which they will receive detailed feedback on their fidelity and skill based on ratings of their audio-recorded sessions using our validated therapy process assessment system, the Yale Adherence and Competence Scale (YACS)⁷⁵. Once certified to begin the trial, the CBT clinicians will meet weekly with a CBT supervisor ([name]), which will involve updating of case material, review of audio recordings of each clinicians’ work, and comparison of self-monitoring of CBT implementation with supervisors’ ratings¹⁴⁵ (see Assessments). This technique, used in our previous psychotherapy studies^{143, 145, 184}, is included to assure fidelity to manual guidelines and a consistent high level of adherence and skill throughout the trial. Clinicians will review and make copies of completed homework assignments and will report, after each session, which CBT modules were covered.

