C.2.f. Data Management and Analyses

The system of data management will include a combination of scannable forms (Teleforms), direct entry interface (Access), and a relational database (SQL Server) within a closed, secure network, allowing data to flow in a continuous cycle of collection, processing, error checking, and correction on a real-time basis while the study is ongoing. Outlined below is the general strategy for data analyses which will address each of our specific aims. Preparatory analyses will include evaluation of baseline equivalence of groups on demographic and prognostic variables, comparability of rates of data availability and treatment exposure across conditions^{239, 240}, *as well as consideration for the potential contribution of assessment reactivity*^{241, 242}. Data analyses will be conducted on the intention to treat sample, and we will attempt to follow all participants regardless of their retention in the treatment arm of the trial^{179, 180}.

Aim 1 - Evaluation of treatment effects:

The principal strategy for assessing the efficacy of the study treatments on outcome will be random effects regression models for continuously measured *primary* (e.g., percentage of days abstinent - PDA) and secondary (e.g., percentage of heavy drinking days, quality of life, etc.) outcomes. Our research group has used these methods to evaluate main and interaction effects, with appropriate covariates (e.g., retention, compliance with treatment) in multiple previous trials^{121, 138, 142, 171, 172}. *We will include treatment utilization data during the follow-up period as a covariate in analyses evaluating treatment effects through follow-up.*

Analysis of treatment effects at post-treatment and follow-up will include the following contrasts:

- **H1a:** *Main effect for CBT on PDA by month during treatment:* Clinician-CBT and CBT4CBT>TAU.
- **H1b:** *Main effect for CBT on PDA by month through follow-up:* Clinician-CBT and CBT4CBT>TAU.

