The procedures for SAE reporting include written documentation using the clinical notes related to the adverse event and specific forms detailing the event with a sign-off by all appropriate supervisory personnel. Communication of recommendations and decisions from all parties (DSMB, Yale Human Investigations Committee, and MCCA or SATU Administration) are made back to the investigator in a timely manner. We will report all protocol amendments or changes in the informed consent form to NIAAA as well as any temporary or permanent suspension of patient accrual.

- d. For multi-site studies for which the Yale PI serves as the lead investigator: **N/A**
 - i. How will adverse events and unanticipated problems involving risks to subjects or others be reported, reviewed and managed?
 - ii. What provisions are in place for management of interim results?

iii. What will the multi-site process be for protocol modifications?

11. Statistical Considerations: Describe the statistical analyses that support the study design.

Aim 1 - Evaluation of treatment effects:

The principal strategy for assessing the efficacy of the study treatments on outcome will be random effects regression models for continuously measured primary (e.g., percentage of days abstinent - PDA) and secondary (e.g., percentage of heavy drinking days, quality of life, etc.) outcomes. Our research group has used these methods to evaluate main and interaction effects, with appropriate covariates (e.g., retention, compliance with treatment) in multiple previous trials^{121, 138, 142, 171, 172}. We will include treatment utilization data during the follow-up period as a covariate in analyses evaluating treatment effects through follow-up.

Analysis of treatment effects at post-treatment and follow-up will include the following contrasts:

- **H1a:** *Main effect for CBT on PDA by month during treatment:* Clinician-CBT and CBT4CBT>TAU.
- **H1b:** *Main effect for CBT on PDA by month through follow-up:* Clinician-CBT and CBT4CBT>TAU.

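### Clinic is neither a listed urn factor nor a prespecified covariate in the H1a/H1b models, which leaves avoidable chance imbalance and some lost precision

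*Combined protocol and SAP*

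**What the plan says.** **Where participants come from.** Section C.2.a (Overview) describes 180 people "seeking treatment for alcohol use at the MCCA program in Bridgeport or New Haven, CT or SATU in New Haven". That is three locations under two organisations.

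**Who delivers treatment.** Under C.2.d (Treatments), TAU is typically "group counseling delivered by masters-level and certified counselors trained and employed by MCCA or SATU and supervised by MCCA Clinic Director" or, at SATU, by that clinic's own director. The CBT clinicians are "at least masters-level clinicians drawn from MCCA or SATU staff and selected on the basis of audio-taped samples of their work". In the CBT4CBT arm the brief weekly monitoring is done by an MCCA or SATU clinician, according to clinic policy.

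**Randomisation.** C.2.c, item 2 (Urn randomization) says the urn is to balance "demographic variables (gender, race, education) as well as likely prognostic variables (severity of alcohol dependence, level of familiarity with and access to computers". These five factors are not introduced as examples, and clinic is not among them.

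**Analysis.** C.2.f (Aim 1), repeated in Section V item 11, plans "random effects regression models for continuously measured" outcomes. The research group is said to have used these methods "with appropriate covariates (e.g., retention, compliance with treatment) in multiple previous trials", and treatment utilization is added as a covariate for the follow-up analysis. Clinic, site and clinician are not named for H1a or H1b. C.2.f also plans a baseline check of demographic and prognostic variables, again without naming clinic. The multi-site items in Section V item 10 and Section VII item 1 are answered as not applicable, so clinic differences are not dealt with there.

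**The concern.** Which organisation a participant attends fixes the content of the comparator and the pool of clinicians in all three arms. It may also go with a different catchment: Section V item 4 gives population figures for MCCA only, so similarity with SATU cannot be assumed. Clinic is known before randomisation and is plausibly related to drinking outcome, which makes it an obvious candidate for balancing and adjustment.

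Two things are at stake. The split of each clinic between arms is left to chance in the one randomisation the trial will have, so part of any clinic difference in PDA can fall into the CBT-versus-TAU contrast. The rest of that difference stays in the residual variance and widens the interval. In addition, because the covariate list is open, whether to include clinic in the primary model could be decided after results are seen.

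**Working it through.** **Inputs from the documents** (C.2.f and Section V item 11): 60 per condition; the two CBT arms pooled against TAU, taken as 120 v 60; d = 0.35 with 3 data points for H1a and d = 0.50 with 7 for H1b; ICC 0.6; alpha 0.05, taken as two-sided because sidedness is not stated; the stated beta of .80 read as power.

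**Assumptions, because the documents are silent:** a clinic's share of the sample, 20-50%; the PDA gap between clinics, 0.3, 0.5 or 0.8 SD.

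**1. The plan's own figure.** The variance of a participant's mean over m measures is (1 + (m-1) x ICC)/m.
- H1a: (1 + 2 x 0.6)/3 = 0.733. SE = sqrt(0.733 x (1/120 + 1/60)) = 0.135 SD. Power = Φ(0.35/0.135 - 1.96) = 0.73, against a stated 0.80.
- H1b: (1 + 6 x 0.6)/7 = 0.657. SE = 0.128 SD. Power = 0.97, against a stated 0.80.

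The stated figures do not reproduce on this reading. That is a separate matter. It is relevant here only because H1a has no spare power on this reading.

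**2. Chance imbalance in a clinic's share.** The 95% limit is 1.96 x sqrt(p(1-p)(1/120 + 1/60)). The shift in the contrast is that limit times the assumed 0.5 SD gap between this clinic and the others.

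| Share p | 95% limit of imbalance | Shift at 0.5 SD | Shift / 0.35 |
|---|---|---|---|
| 0.2 | 0.124 | 0.062 SD | 18% |
| 0.3 | 0.142 | 0.071 SD | 20% |
| 0.5 | 0.155 | 0.078 SD | 22% |

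Against the H1a standard error, 0.062/0.135 = 0.46 and 0.078/0.135 = 0.58, so the limit is about half a standard error.

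**3. Simulation.** 180 individually randomised participants (120 CBT, 60 TAU), three clinics with shares of one third each or 50/30/20, the gap taken from best to worst clinic with the third halfway between, and 8,000 runs per scenario, analysed with and without fixed clinic terms.
- Mean bias: 0.00 SD in every scenario.
- Type I error, averaged over randomisations: 4.6-5.4% without clinic terms and 4.5-5.3% with them.

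| Gap | 95% limit of chance shift | H1a power without clinic | H1a power with clinic |
|---|---|---|---|
| 0.3 SD | 0.04 SD | 0.72-0.73 | 0.72-0.73 |
| 0.5 SD | 0.06 SD | 0.71 | 0.72-0.73 |
| 0.8 SD | 0.10 SD | 0.67-0.68 | 0.72 |

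**4. Hand check of the unadjusted power.** With three equal, evenly spaced clinics the between-clinic variance is gap²/6, that is 0.015, 0.042 and 0.107. Adding this to 0.733 and repeating step 1 gives power of 0.725, 0.710 and 0.675, in line with the table.

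**Limits.** The simulation uses simple random allocation rather than the urn, so any indirect balance on clinic through race, education or severity is ignored. It assumes the same treatment effect in every clinic and does not model clustering by clinician.

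**The case against.** The strongest reply is that randomisation already deals with this. Participants are randomised individually and nothing ties an arm to a clinic, so the expected bias is zero. The chance shift is also part of the random error that the confidence interval covers (half-width 1.96 x 0.135 = 0.27 SD), not something on top of it. This stands. A reader might infer that clinic is confounded with treatment, so that a clinic difference can systematically pass for a treatment effect; neither the documents nor the calculation supports that.

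Three further points also stand.
- A reader might infer three clinics, each with its own TAU, staff and supervisor. The text shows two organisations and two TAU directors, and nothing gives the two MCCA locations separate arrangements.
- A reader might infer that the model rules clinic out. Its covariates are given as examples, so clinic is unspecified rather than excluded.
- A figure of about 25% of d = 0.35 can be reached by comparing one CBT arm with TAU (60 v 60: 1.96 x sqrt(0.25 x 2/60) x 0.5 = 0.089 SD). The power table attaches d = 0.35 to the pooled contrast, for which the range is 18-22%.

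There is partial protection as well: race, education and severity are urn factors, the CBT clinicians share a manual, certification and trial supervision, and the monitoring follows a manual. This makes large clinic gaps less likely but does not balance or adjust for TAU content, which stays specific to each organisation.

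What the reply does not answer is that chance error from a known baseline factor can be removed at almost no cost, and that an open covariate list leaves the primary model undecided.

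**Conclusion.** The point holds as an omission in design and prespecification, not as a source of bias. The absence of clinic from the urn factors and from the named covariates is plain in the text. The size of the consequence rests on assumed clinic shares and gaps. At a 20-50% share and a 0.5 SD gap, the 95% limit of the chance shift in the pooled contrast is about 0.06-0.08 SD. The power recovered by clinic terms is about nil at a 0.3 SD gap, 1-2 points at 0.5 SD and 5 points at 0.8 SD. If the clinics differ little, little is lost. The change is still worth making: H1a power is nearer 0.73 than 0.80 on a two-sided pooled reading, and the plan currently gives no view of whether the effect depends on one clinic's TAU.

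**What to change.** - **Model.** State in C.2.f and Section V item 11 that clinic is a fixed effect in the H1a and H1b models for all participants, including those already randomised. Use the three locations, or organisation if a location turns out too small, and fix that rule before unblinded results are seen.
- **Urn.** Add clinic as a factor for any remaining randomisations, if enrolment is still open. The documents do not state enrolment status, and the project period of April 2016 to July 2021 may make this step moot.
- **Reporting.** Give the arm contrast by clinic descriptively. A clinic main effect or an urn factor does not show whether the effect varies with one clinic's TAU; this table is the only part of the fix that bears on it.

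**Cost.** One sentence in the analysis plan and two degrees of freedom (one if organisation is used) out of about 180. Adding clinic to the urn is one more factor in the existing program, at the price of slightly looser balance on the other five. No extra participants or procedures are needed.
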